Step 2. If the scheduled assessment is not completed or is not evaluable (i.e. not readable or non-diagnostic), this assessment will be censored (or excluded from proceeding to the next step).

Step 3. If a visit has multiple DUS or angiographic assessments, the following hierarchical criteria will be used to identify the appropriate assessment for that visit:

- Choose the one that has a positive observation(s) – i.e. significant reduction of blood flow, etc.; if more than one assessment contains at least one positive observation, the earliest assessment will be used;
- If none of the assessments has positive observations, choose the one that is the closest to the scheduled visit date

Step 4. If a visit has both DUS assessment and angiographic assessment, the following hierarchical criteria will be used to identify the appropriate assessment for that visit to use in the analysis:

- If there are multiple DUS assessments or multiple angiographic assessments that are slotted in the same visit window, please refer to step 3 to select one non-missing assessment for DUS and/or angiography separately. Please refer to the following table for the assessment and outcome determination

DUS assessment	Angiographic assessment	Final selected assessment	Final selected assessment outcome
Success	Failure	Angiography	Failure

Success	Success	Choose the one that is the closest to or earlier than the scheduled visit date	Success
Success	Missing	DUS	Success
Failure	Failure	Choose the one that is the closest to or earlier than the scheduled visit date	Failure
Failure	Success	Angiography	Success
Failure	Missing	DUS	Failure
Missing	Failure	Angiography	Failure
Missing	Success	Angiography	Success
Missing	Missing	N/A	Missing

As stated previously and shown in the hierarchy above, in cases where both angiography and DUS are available at the same assessment and they provide different conclusions then angiography will be preferentially used.

The step-by-step description of the above hierarchical criteria in determining the 1 and 6-month site assessments is as follows:

- 1) Remove the assessments with value of 'N/A' or 'missing'. If the assessment result is N/A or missing, then delete (e.g., set the value to 'missing');

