- 2) Data will be used for subjects who have an evaluable (readable) scheduled or unscheduled DUS or scheduled or unscheduled angiography. Failure of patency can occur at any time post-procedure. Choose the first occurrence of angiography for failure. If no angiography failure, then choose the first occurrence of DUS failure. If there are no failures, but there are success(es) then choose the last successful occurrence of angiography and if no angiography then use the last successful occurrence of DUS. If there are no DUS or angiography assessments, then set the value to 'missing'.

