5.21 Primary Patency

Censor any DUS or angiogram assessments taken after any TVR as a revascularization changes the vessel making it unevaluable. If the date of assessment > date of TVR, then delete (e.g., set the value to 'missing').

At the time of a CD TLR set primary patency to failure.

Once a failure of primary patency has occurred in a subject all future time points reporting primary patency will be set to failure. If there are no failures and one or more successes, then the subject is a success up to the time of the last success recorded.

Unique composite endpoint such as primary patency contains both site-reported imaging endpoint and clinical/safety endpoint (by cut-off days), the event of the

individual components will be determined first, and the composite endpoint will then be determined as the following:

Freedom from significant stenosis/occlusion within 1-Month	Freedom from CD TLR within 37 Days	1-Month Primary Patency
Yes	Yes	Yes
Yes	No	No
Yes	Missing Data	Missing Data
No	Yes	No
No	No	No
No	Missing Data	No
Missing Data	Yes	Missing Data
Missing Data	No	No
Missing Data	Missing Data	Missing Data

Primary Patency at 6 months follow-up will be determined following similar convention specified above for 1 month.

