5.22 Primary-assisted Patency

If a subject is a success on primary patency, then they are a success on primary-assisted patency and require no further evaluation via this algorithm. If a subject is a failure on primary patency without a subsequent TVR then they are a failure on primary-assisted patency and require no further evaluation via this algorithm. Subjects failing primary patency for a significant stenosis diagnosed via imaging and undergoing a TLR will be assessed following the TLR for primary-assisted patency by the algorithm below.

Unique composite endpoint such as primary-assisted patency contains both site-reported imaging endpoint and clinical/safety endpoint (by cut-off days), the event of the individual components will be determined first and the composite endpoint will then be determined as the following (apply to primary patency failure subjects following TLR for significant stenosis only):

Freedom from significant stenosis/occlusion within 1-Month	Freedom from 2 nd CD TLR within 37 Days	1-Month Primary-assisted Patency
Yes	Yes	Yes
Yes	No	No
Yes	Missing Data	Missing Data
No	Yes	No

Freedom from significant stenosis/occlusion within 1-Month	Freedom from 2 nd CD TLR within 37 Days	1-Month Primary-assisted Patency
No	No	No
No	Missing Data	No
Missing Data	Yes	Missing Data
Missing Data	No	No
Missing Data	Missing Data	Missing Data

Once a failure of primary-assisted patency has occurred in a subject by the algorithm above then all future time points reporting primary-assisted patency will be set to failure. If there are no failures and one or more successes, then the subject is a success up to the time of the last success recorded.

Primary-assisted patency at 6 months follow-up will be determined following similar convention specified above for 1 month.

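### The SAP's patency rules conflict for a failing duplex with a successful angiogram, and leave some re-treated subjects without a stated primary-assisted or secondary patency result (minor; secondary endpoints only)

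*SAP*

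**What the plan says.** **Choosing the image (SAP 5.2).** Step 1 sets analysis windows of days 15–60 for the 1-month visit and days 61–210 for the 6-month visit. Step 4 begins "If a visit has both DUS assessment and angiographic assessment, the following hierarchical criteria will be used to identify the appropriate assessment for that visit", and its table gives an outcome for each of nine duplex/angiogram combinations. The section states its preference for angiography twice; the second time it says "in cases where both angiography and DUS are available at the same assessment and they provide different conclusions then angiography will be preferentially used". It then introduces a two-item list: "The step-by-step description of the above hierarchical criteria in determining the 1 and 6-month site assessments is as follows". Item 1 removes missing results. Item 2 admits scheduled and unscheduled imaging, allows failure at any time after the procedure, and continues: "Choose the first occurrence of angiography for failure. If no angiography failure, then choose the first occurrence of DUS failure". A success is chosen only if there is no failure of either kind.

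**Deriving patency (SAP 5.21 to 5.23).** Section 5.21 carries failure forward: "Once a failure of primary patency has occurred in a subject all future time points reporting primary patency will be set to failure". It also sets primary patency to failure at a clinically-driven TLR. Section 5.22 has a default, "If a subject is a failure on primary patency without a subsequent TVR then they are a failure on primary-assisted patency", and a table limited in these words: "apply to primary patency failure subjects following TLR for significant stenosis only". Section 5.23 has the same default for secondary patency. Its own table is limited to re-treatment for total occlusion, called TLR in the text and TVR above the table.

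**Failure criterion.** Section 5.2 assigns the stenosis component to primary and primary-assisted patency, and the occlusion component to primary and secondary patency. The first column of the 5.23 table uses stenosis and occlusion together.

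**The concern.** An analysis plan should give one value for one set of data. Here two stated rules give opposite values for one imaging pattern, and some re-treated subjects have no stated value at all. Two programmers could follow the SAP faithfully and report different patency rates, or the choice could be made after the data are seen. Re-treated subjects are the ones who separate primary-assisted and secondary patency from primary patency, so the gaps fall where these two endpoints do their work.

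**Working it through.** **1. Step 4 table against item 2, both modalities in one visit window**

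| Duplex | Angiogram | Step 4 table | Item 2 |
|---|---|---|---|
| Success | Failure | Failure | Failure |
| Success | Success | Success | Success |
| Success | Missing | Success | Success |
| Failure | Failure | Failure | Failure |
| Failure | Success | Success | **Failure** |
| Failure | Missing | Failure | Failure |
| Missing | Failure | Failure | Failure |
| Missing | Success | Success | Success |
| Missing | Missing | Missing | Missing |

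The outcomes conflict in one row of nine. On the Success/Success and Failure/Failure rows only the chosen image can differ: the table goes by closeness to the visit date, whereas item 2 takes the angiogram.

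The pair itself is also not fixed. The text speaks of the same assessment, while the table works by visit, so images weeks apart can be paired.

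**2. Imaging outside the windows.** Take a subject discharged before day 10 with a failing duplex on day 10 and a successful duplex on day 30. Day 10 lies in no analysis window, so Steps 1 to 4 give a 1-month success. Item 2 gives failure. This needs no second modality.

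**3. What follows from a failure.** Section 5.21 carries it to later time points, and 5.22 and 5.23 inherit it when no TVR follows. One 1-month discordant pair can therefore change up to 3 endpoints × 2 time points = 6 reported results.

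**4. Results stated for primary-patency failures**

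| Cause of primary failure | Later re-treatment | Primary-assisted (5.22) | Secondary (5.23) |
|---|---|---|---|
| Stenosis | None | Failure | Failure |
| Stenosis | TLR | 5.22 table | **None stated** |
| Occlusion | None | Failure | Failure |
| Occlusion | TLR | **None stated** | 5.23 table |
| Clinically-driven TLR, no failing image | That TLR | **None stated** | **None stated** |
| Stenosis | TVR outside target lesion only* | None stated | None stated |
| Occlusion | TVR outside target lesion only* | None stated | Unclear: text says TLR, table heading says TVR |

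*These rows exist only if TVR is broader than TLR; the SAP does not define TVR.

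Reading TVR as excluding TLR does not close the gaps. The default sentence would then fail every TLR-only subject, while the next sentence sends some of them to the table.

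**5. Secondary patency criterion.** A re-treated occlusion that is later stenosed but open is a failure in the 5.23 table. It would not be one if secondary patency depended on occlusion alone, as 5.2 reads. The 5.23 default likewise fails a non-occluded stenosis that was never re-treated.

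**6. Size.** The change per discordant subject is 100/n percentage points. With the full planned enrollment, 100/121 = 0.83. This is a floor, because n will be smaller. SAP 4.3 removes subjects with a non-qualifying lesion from subject-level effectiveness endpoints, patency is listed as subject level, and 5.2 excludes subjects without evaluable imaging. As an assumed illustration, three discordant subjects would move patency by at least 3/121 = 2.5 points.

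**The case against.** The strongest reply is that the intended answer to the imaging conflict is evident. The preference for angiography appears twice in text and again in the table. Item 2 speaks of first and last occurrences, which are terms about time, so it could be meant to act on the image already chosen at Step 4. That makes item 2 the passage out of line and points to a drafting slip. But the SAP does not say that item 2 comes after Step 4; it calls the list a description of the hierarchy, and item 1 repeats the removal of missing images. The literal conflict stands.

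Second, Protocol Table 6 asks for duplex or angiography at each visit, so paired images may be few. A clinically-driven TLR without a failing image may also be rare, since SAP 2.1 defines such a TLR by restenosis on imaging. It can still arise where no evaluable site-reported image shows the failure. Both remarks limit the size of the problem without supplying a rule.

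Third, TLR and TVR may be used interchangeably, as 5.23 suggests. If so, the two starred rows disappear. The missing results for re-treated stenoses, re-treated occlusions and TLR without a failing image remain.

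A reader might also infer that secondary patency will come out below primary-assisted patency and is therefore invalid. The documents do not support that. They state no required order between the two, and give no patency or re-treatment rates from which to calculate either.

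**Conclusion.** The point holds as a minor one. On the text alone, one imaging pattern has two opposite stated outcomes, out-of-window failures are treated inconsistently, three groups of re-treated results are missing, and secondary patency has two criteria. A further gap depends on TVR being broader than TLR.

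The scope is secondary, site-reported endpoints 8 to 10. A reader might infer that study success is at risk; it is not. Technical success and 30-day freedom from MAE do not use these algorithms, and the patency endpoints carry no hypothesis or success criterion.

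The total size is unknown. The only firm figure is the floor of about 0.8 points per discordant subject, and the number of such subjects cannot be derived from the documents.

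**What to change.** - **Item 2 (SAP 5.2).** State that it applies only after Step 4 has resolved discordant pairs in favour of angiography. Define the pair once, as the same assessment or the same window, in both text and table. State how imaging outside the analysis windows is handled.
- **Sections 5.22 and 5.23.** Use one re-treatment term in the default sentence, the routing sentence and the table heading. Give every re-treated primary-patency failure an explicit result in both endpoints: re-treated stenosis, re-treated occlusion, and TLR without a failing image. If TVR is broader than TLR, also cover TVR outside the target lesion and say whether imaging after it counts. For primary patency, 5.21 already rules on this: "Censor any DUS or angiogram assessments taken after any TVR as a revascularization changes the vessel making it unevaluable".
- **Secondary patency criterion.** Use one imaging failure criterion in 5.2, in the 5.23 table and in the 5.23 default.

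The result for each group and the choice of criterion are the sponsor's decisions, to be fixed before the patency analysis. The cost is SAP wording and programming, with no new data, visits or imaging.

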5.21 Primary Patency

Censor any DUS or angiogram assessments taken after any TVR as a revascularization changes the vessel making it unevaluable. If the date of assessment > date of TVR, then delete (e.g., set the value to 'missing').

At the time of a CD TLR set primary patency to failure.

Once a failure of primary patency has occurred in a subject all future time points reporting primary patency will be set to failure. If there are no failures and one or more successes, then the subject is a success up to the time of the last success recorded.

Unique composite endpoint such as primary patency contains both site-reported imaging endpoint and clinical/safety endpoint (by cut-off days), the event of the

individual components will be determined first, and the composite endpoint will then be determined as the following:

Freedom from significant stenosis/occlusion within 1-Month	Freedom from CD TLR within 37 Days	1-Month Primary Patency
Yes	Yes	Yes
Yes	No	No
Yes	Missing Data	Missing Data
No	Yes	No
No	No	No
No	Missing Data	No
Missing Data	Yes	Missing Data
Missing Data	No	No
Missing Data	Missing Data	Missing Data

Primary Patency at 6 months follow-up will be determined following similar convention specified above for 1 month.

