2. ENDPOINT DEFINITIONS

2.1 Primary Safety Endpoint

The primary safety endpoint is a composite endpoint triggered by the occurrence of any five categories of events through 30 days after the index procedure¹. These events are the following:

1. All-cause mortality- Death from any cause, from the point of enrollment through 30 days.
2. Clinically-driven TLR- Any revascularization of the target lesion that occurs after the subject has left the procedure room following the index procedure. TLR do not include adjunctive interventions performed during the index procedure, whether planned or for failed atherectomy or for complications of atherectomy. TLRs are considered to be clinically-driven when they occur as a result of restenosis >50% diameter reduction as measured angiographically or by duplex ultrasound (occlusion or stenosis with Peak Systolic Velocity Ratio >2.4)².
3. Perforation of the target vessel- Imaging evidence (standard contrast angiography, computed tomography angiography or open surgical/pathology visualization) of target vessel perforation from any cause. For angiography and CTA, perforation is defined by contrast extravasation outside of the adventitia.
4. Clinically- significant distal embolization- Target limb embolization documented on core laboratory- assessed angiography or with open surgery/pathology, accompanied by symptoms referable to the involved vascular bed.
5. Major amputation- Amputation of the target limb that results in limb shortening; i.e. is performed at or above the level of the malleoli.

The composite endpoint and each individual component are all subject level endpoints.

¹ The index procedure is considered to occur on day 0; the first post-procedure day is day 1, and so on. The 30-day time point includes any events with a start date prior to 11:59PM on day 30.

² If an angiogram and a duplex ultrasound imaging study are discordant within any 30-day period, the angiographic results will supersede the duplex findings.

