2.1 Secondary Endpoints

Secondary endpoints will consist of the following with level of analysis in parentheses:

- 1) Change in percent stenosis after treatment with RevolutionTM Peripheral Atherectomy System, determined after atherectomy and prior to other adjunctive therapies, as measured by the angiographic core laboratory (lesion level);
- 2) Procedural success as defined by target lesion residual stenosis of $<30\%$ at the conclusion of the index procedure, after atherectomy and any adjunctive endovascular treatment, as measured by the angiographic core laboratory (lesion level);
- 3) Assessment of the individual components of the primary safety endpoint (MAE); including all-cause mortality, major target limb amputation, clinically significant distal embolization, major target vessel perforation requiring surgical or endovascular repair, and clinically-driven TLR, measure through 30 days and at 6 months (subject level);
- 4) Minor unplanned target limb amputation rate through 30 days and 6 months (subject level);
- 5) Myocardial infarction through 30 days and 6 months (subject level);

³ The shoulder-to-shoulder length is determined visually using a Quantitative Vascular Angiography (QVA) software application. RVD is determined at the location of the MLD, linearly interpolated between the luminal diameters just proximal to and distal to each shoulder.

- 6) Incidence of target vessel revascularization (TVR) through 30 days and 6 months (subject level);
- 7) Frequency of angiographic procedural distal embolization (symptomatic) in the target limb as confirmed angiographically by the core laboratory (subject level);
- 8) Primary patency of the target lesion at 30 days and 6 months, determined by duplex ultrasound or angiography (subject level);
- 9) Primary-assisted patency of the target lesion at 30 days and 6 months, determined by duplex ultrasound or angiography (subject level);
- 10) Secondary patency of the target lesion at 30 days and 6 months, determined by duplex ultrasound or angiography (subject level).

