5.2 Effectiveness Endpoints

Patency effectiveness endpoints (site-reported endpoints) include the endpoints that are determined by site assessment (DUS or angiography), such as the significant stenosis/occlusion measured by DUS or angiography as well as consideration of the clinical endpoint – TVR. Such site-reported endpoints rely on the actual evaluable assessment. If the scheduled assessment is not completed or the data is not evaluable (i.e., not readable, or non-diagnostic), it will be treated as missing value and will be excluded from the analysis.

The significant stenosis component for the patency endpoints (primary patency and primary-assisted patency) is determined by a qualified angiogram diameter stenosis (DS) $\geq 50\%$ and $<100\%$ evaluated by the site or qualified DUS evaluated as DUS category ‘50-99%’ that is evaluated by the site-reported DUS. The occluded component of primary and secondary patency endpoints is determined by a qualified angiogram DS=100% or qualified DUS evaluated as ‘occluded’. Either significant stenosis or occlusion will be considered failure of primary patency.

Data will be used for subjects who have an evaluable (readable or diagnostic) scheduled or unscheduled DUS or angiographic assessment (site-reported imaging assessments) that will be based on reporting windows described below. To minimize the missing assessment at 1 and 6-month visits, analysis windows provided below will be utilized.

Given that angiography is a more precise visualization of the vessel than DUS, in cases where both angiography and DUS are available at the same assessment and they provide different conclusions then angiography will be preferentially used in the algorithm.

Step 1. For convention, the imaging visits use the following reporting windows. The study day used in the window definitions is calculated as “assessment date” minus “Index procedure date”:

Study Visit	Target Day	Compliance Reporting Windows	Analysis Reporting Windows
Index Procedure	Day 0	N/A	N/A
Discharge	Discharge	N/A	1-discharge
30-days	Day 30	Study Day 23 – 37	15-60
6-month	Day 180	Study Day 166 – 194	61-210

These reporting windows serve 2 primary functions:

- 1) Allow for the calculation of compliance to imaging follow-up for each visit – compliance reporting window ranges.
- 2) Provide the analysis reporting windows for patency endpoints at key follow-up time points.

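### SAP 5.21 discards every scan after any target vessel revascularization, so a later failure of a target lesion that was not re-treated can drop out of 6-month primary patency

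*SAP*

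**What the plan says.** SAP 2.1 (Secondary Endpoints) lists primary patency of the target lesion at 30 days and 6 months, analysed per subject. SAP 5.21 gives the algorithm:

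- **Deletion.** "Censor any DUS or angiogram assessments taken after any TVR as a revascularization changes the vessel making it unevaluable". The programming line is "If the date of assessment > date of TVR, then delete", so a scan on the TVR date itself is kept. The rule names no lesion.
- **Failure by revascularization.** "At the time of a CD TLR set primary patency to failure". The clinical column of the composite table is "Freedom from CD TLR within 37 Days". No other revascularization appears in the table.
- **Missing imaging.** When imaging is missing and the subject is free of CD TLR, the table returns missing. SAP 5.2 says of an assessment that was not done or not evaluable that "it will be treated as missing value and will be excluded from the analysis".

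SAP 2.1 (Primary Safety Endpoint) defines the clinically driven event by anatomy: "TLRs are considered to be clinically-driven when they occur as a result of restenosis >50% diameter reduction", or the duplex equivalent. SAP 5.2 names TVR, not CD TLR, as the clinical element of patency. Neither document defines TVR beyond spelling out the abbreviation.

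**The concern.** The event that triggers deletion is wider than the event that counts as failure, and wider than the endpoint. A TVR elsewhere in the artery says nothing direct about the target lesion, yet every later scan of that lesion is removed. If one of those scans shows the lesion narrowed or occluded and no CD TLR follows, a documented loss of patency does not reach the result.

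The reason given is that revascularization makes the vessel unevaluable. That does not fit a lesion that was not treated and can be seen. SAP 5.22 and 5.23 also go on to evaluate imaging after a TLR, so the plan itself regards even a re-treated lesion as assessable. There is a sound reason to stop crediting a re-treated lesion to primary patency, namely that it is no longer unassisted. That reason does not extend to an untouched lesion.

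Because the rule works on dates alone, a TVR for one lesion also removes later scans of the subject's other target lesions. Several target lesions in one limb are allowed (Protocol 6.3), and 1.5 per subject are assumed (SAP 3.3). At stake is the credibility of the 6-month primary patency figure.

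**Working it through.** The plan states no patency rate, TVR rate or patency sample size, so there is no figure to reproduce. The check traces subjects through the rule and then illustrates the size.

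**1. Tracing the rule at 6 months.** Inputs are the deletion and failure rules and the composite table (SAP 5.21) and the analysis window of days 61–210 (SAP 5.2). The 6-month cutoff for CD TLR is not stated. Day 194 is assumed, by analogy with the 37 days used at 1 month; each is the upper limit of its compliance window.

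| Course | SAP 5.21 | Later scans kept |
|---|---|---|
| Patent day 30; TVR away from the lesion day 90; lesion occluded day 180 | Missing | Failure |
| Same, but lesion patent day 180 | Missing | Success |
| Patent day 30; TVR away from the lesion day 90 with patent same-day angiogram; occluded day 180 | Success | Failure |
| Failing scan day 88; TVR day 90 | Failure | Failure |
| TVR away from the lesion day 90; CD TLR day 150 | Failure | Failure |
| CD TLR day 90 | Failure | Failure |

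In row 1 the day-30 scan belongs to the 15–60 window and the day-180 scan is deleted. No imaging remains in days 61–210, and missing imaging with freedom from CD TLR gives missing. In row 3 the same-day patent scan survives, lies in the window and stands as the outcome. The last three rows mark where the rule does no harm.

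At 1 month, a TVR on day 10 followed by an occlusion on day 30 gives missing instead of failure.

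**2. Illustration of size (every rate is assumed).** Let N = 110 subjects have 6-month imaging, S = 80 be truly patent, m = 6 have a TVR that spared the target lesion, and k of those 6 be patent at 6 months.

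- All scans kept: S/N = 80/110 = 72.7%.
- SAP 5.21, all 6 dropped: (S − k)/(N − m).
  - k = 3: 77/104 = 74.0% (+1.3 points)
  - k = 0: 80/104 = 76.9% (+4.2)
  - k = 6: 74/104 = 71.2% (−1.6)
- SAP 5.21, all 6 kept as successes through an earlier in-window patent scan: (S − k + m)/N.
  - k = 3: 83/110 = 75.5% (+2.7)
  - k = 0: 86/110 = 78.2% (+5.5)

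When subjects are dropped, the error changes sign where k/m = S/N, that is at k = 6 × 80/110 = 4.4. Patency is overstated only if these subjects do worse than the whole group.

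**3. Wider range.** Take about 80% patency in the other subjects; 2, 6 or 11 of 110 with such a TVR; and 25% to 100% of those failing later, rounded to whole subjects.

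- Dropping them reports 79.6% to 79.8%. Keeping scans gives 71.8% to 80.0%.
- Lowest error: 86/108 = 79.6% against 88/110 = 80.0%, or −0.4 points.
- Highest error: 79/99 = 79.8% against 79/110 = 71.8%, or +8.0 points.
- If the 11 are scored as successes: 90/110 = 81.8%, or +10.0 points.

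**The case against.** Much can be said for the plan, and most of it stands.

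- **Failures still caught.** A failing scan on or before the TVR date counts and is carried forward. A later CD TLR counts too. The loss is confined to failures first seen after the TVR and not treated by CD TLR.
- **TLR that is not clinically driven.** A reader might infer that every TLR must be scored as failure. The documents do not support that. A clinically driven TLR requires restenosis above 50%, so a TLR that is not clinically driven was mostly done on a lesion still patent by the plan's own threshold. Failing it would define a different endpoint.
- **Conflict within the SAP.** A reader might also see a contradiction with SAP 5.2, step-by-step item 2: "Failure of patency can occur at any time post-procedure". Item 2 is a general rule for evaluable scans, and 5.21 is a specific rule that narrows it. That is not a contradiction.
- **Imaging before the TVR.** Protocol Table 6 requires imaging at unscheduled visits prompted by target-limb symptoms, so many subjects will have a scan on or before the TVR date. This reduces losses from the denominator, but a patent scan of that kind can also turn a later failure into a success.
- **30-day result.** Exclusion criterion 6 bars endovascular procedures in the target vessel planned within 30 days, so the 1-month effect needs an early unplanned TVR and should be small.
- **Visibility.** TVR incidence is reported as its own secondary endpoint, so reintervention is not hidden.

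None of this covers an untouched target lesion seen to fail after a TVR elsewhere, for which 5.21 makes no exception.

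**Conclusion.** The point holds in a limited form. As written, SAP 5.21 gives a wrong result for a named secondary endpoint whenever a TVR spares a target lesion, that lesion later fails on imaging, and no CD TLR follows. The mismatch between 5.2 (TVR) and 5.21 (CD TLR) adds avoidable ambiguity.

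Upward bias in 6-month primary patency is likely but conditional: it requires these subjects to have worse later patency than the rest. In the main illustration the overstatement is 1.3 to 4.2 points if they are dropped. It turns negative if nearly all of them stay patent. These figures rest on assumed TVR and failure rates, since the documents give neither.

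A reader might infer that the trial's conclusion is at risk. It is not: primary patency carries no hypothesis test or performance goal, and the success criteria in SAP 4.5 rest on the two primary endpoints only.

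**What to change.** - In SAP 5.21, delete scans only for a target lesion that was itself re-treated, and only after that re-treatment.
- Keep all evaluable scans, patent and failing alike, of target lesions the TVR did not treat. Keeping only the failing ones would select by outcome and push patency down.
- Define TVR, and align SAP 5.2 with 5.21 on whether TVR or CD TLR is the clinical element of patency. Since deletion becomes lesion-specific, state how several target lesions combine into the subject-level result.
- Add a sensitivity analysis that counts any TVR as loss of primary patency.

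Protocol 8.6 already requires any intervention on the initially treated lesion to be recorded on the Additional Treatment CRF. Those data should identify whether the target lesion was treated. The CRFs are not among the documents, so this should be confirmed before programming.

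The cost is a few lines of SAP text and a little more programming. Reported patency may be slightly lower.
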